Measurements	Total intraoperative and postoperative opioid administration during hospitalization will be recorded from the patient's electronic medical record (EMR). Pain intensity will be assessed using the Numeric Rating Scale (NRS) and colored-visual analogue scale. Pain relief will be assessed using five point scale (0-no relief, 4-complete pain relief). Postoperative sedation will be recorded using Modified Observer's Assessment of Alertness/Sedation (MOAA/S). Assessment of opioid side effects will be performed using Opioid-Related Symptom Distress Scale (ORSDS). Daily opioid consumption and daily pain self-assessments using a colored-visual analogue scale will be recorded in a home diary for approx 30 days following surgery (from hospital discharge until postop clinic visit). Additional ORSDS assessments will be recorded at various timepoints (approx 7, 14 and 30 days postop) in the home diary. Subjects may have their CYP2B6 genotype determined.

Statistical Methodology	Demographic data including race, sex, and age will be analyzed using chi-square and t- test or ANOVA, as appropriate. Baseline characteristics of the cohort will be described. Total daily opioid consumption and pain scores using NRS, will be compared between the groups. Outcome measures will be expressed as the mean and standard deviation. Group outcomes will be compared across the two groups, using t-test and/or analysis of variance, ANOVA and MANCOVA to account for potential cofounders.
Outcomes	
Primary: Intraoperative and postoperative opioid utilization
 
Secondary:
 
 1) Opioid consumption and pain relief within first 30 postoperative days 2) Pain scores and pain self-assessments 3) Influence of CYP2B6*6 genotype on methadone clinical effectiveness for pain relief and opioid consumption

1. Specific Aims

- 1.1. To study the effects of a single dose of methadone on postoperative pain and opioid consumption in patients undergoing moderately painful, ambulatory surgical procedures.
- 1.2. Determine opioid consumption and pain relief within first 30 postoperative days
- 1.3. Determine cytochrome P4502B6 (CYP2B6) genotype in patients receiving methadone, and any relationship to postop pain relief and opioid consumption

2. Background

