pain relief). Observed sedation (Modified Observer's Assessment of Alertness/Sedation, MOAA/S) and subject's self-assessment of sedation are recorded at the same intervals as pain assessments. Assessment of opioid side effects is performed at approximately 24 hrs or prior to discharge from the hospital using Opioid-Related Symptom Distress Scale (ORSDS). The total amount of other drugs administered during hospitalization for prophylaxis or treatment of opioid side effects will be recorded from the EMR. Daily home opioid usage and pain self-assessments will be recorded in a home diary. The ORSDS assessments will also be completed at various timepoints (approximately 7, 14 and 30 days postop).

Any adverse events are described, recorded and reported according to GCP and IRB regulations.

7. Data Collection and Monitoring.

Opioid Consumption During Hospitalization

The EMR will be used to calculate the amount of morphine or morphine equivalents administered during surgery and until discharge, as well as other drug administration for treatment and/or prophylaxis of possible opioid side effects.

Follow-up Assessments

A home diary will be used to assess daily drug dosing history upon discharge from the hospital until the patient's postop clinic visit at approximately 30 days. Subjects will also record daily pain self-assessments using a colored-visual analogue scale (at rest, with activity and with coughing). The ORSDS will be completed and recorded on approximately the 7th, 14th and 30th day. We will also ask subjects about remaining number of pain medications and their disposal at the 30 day time point.

CYP Genotyping

Approximately 5 ml of blood will be collected from an IV line for CYP2B6 genotyping. Genotyping will be performed at the WUSTL Genome Technology Access Center (GTAC).

Other Measurements

Required baseline measurements that will be obtained from the EMR are age, vital signs, weight, height, and peripheral oxygen saturation by pulse oximetry and are all collected as standard of care.

8. Data and Safety Monitoring Plan.

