In general, the Department of Anesthesiology has developed a specific set of Standard Operating Procedures (SOPs) for clinical research. All individuals working on study are required to read and be totally familiar with and compliant with the SOPs. The SOPs are in part developed from and are compliant with the Institutional guidelines, including those for a) Interactions with the Washington University Human Subjects Review Committee, b) Informed Consent Development and Implementation, c) Subject Recruitment and Screening, d) Subject Management While on Study, e) Adverse Event Reporting. The specific plan for submitting Adverse Event Reports to the IRB is detailed in the SOP for Adverse Event Reporting.

The specific monitoring plan for this investigation is commensurate with the risks, size and complexity of the investigations planned. The potential risks are attributable to the use of methadone. Based on the small size and relatively low risks nature of the protocol, only the PI and CoI are involved in monitoring plan, rather than a full DSMB. These individuals will review the annual summary of adverse events. In addition, they will review all reports of a Serious Adverse Event, or an Unexpected Adverse Event.

9. Statistical Methods

Primary Assessment

Overall opioid (morphine equivalents) consumption for each patient during hospital stay
Absolute pain and sedation scores

CONFIDENTIAL: This document is the intellectual property of [name]. Acceptance of this document constitutes the agreement by the recipient that no unpublished information contained herein will be published or disclosed without prior written approval.

Secondary Assessments

Opioids (morphine equivalence) consumption within approx. first 30 postoperative days
 Postoperative pain self assessments
 CYP2B6*6 Genotype

Analysis

Sample Size: Our initial plan is to enroll ≥ 60 evaluable subjects in each of two cohorts for this pilot study. More specifically, this pilot plans 20 evaluable subjects in each methadone group within each cohort, with requisite proportional controls. Total number in each of the two cohorts will reflect the number of dose groups in each cohort (per escalation). Anticipated total evaluable is <200 .

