Statistical Analysis: Each cohort is analyzed separately. Baseline characteristics of each cohort and groups within each cohort will be described. Demographic data including race, sex, and age at study entry will be analyzed using chi-square and t-test or ANOVA, as appropriate. Total daily opioid consumption and pain scores using NRS will be compared between the groups. Outcome measures will be expressed by the mean and standard deviation. Group outcomes will be compared across the two groups, using t-test and/or analysis of variance, ANOVA and MANCOVA to account for potential cofounders.

10. Risk Assessment

Methadone

The most common side effect of opioids such as methadone is mild sedation. Since patients will be anesthetized during this period, clinical methadone effects are expected to be no different from those of anesthesia and any other opioid administered during anesthesia. The most common adverse effect of methadone is nausea and/or vomiting. Patients will have only clear liquids 6 hours before anesthesia, per standard of care. If nausea and/or vomiting occur, they will be treated using the standard of care for all post-anesthesia nausea and vomiting. Respiratory depression is a potential concern with all opioids, but has not been problematic at the doses of methadone that have been used in similar previous studies. Mild respiratory depression is defined as respiratory rate <8 /min in adults. Severe depression will be defined as the administration of naloxone to a patient with respiratory rate < 6 /min. If treatment is required, naloxone will be used. Patients in the hospital are routinely periodically monitored by blood pressure and/or pulse oximetry, and receive supplemental oxygen if dictated, according to good clinical practice.

Special Precautions

Standard of care for all surgical patients includes an IV, pulse oximetry, ECG, blood pressure monitoring.

Genotyping

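### Section 9 ranks pain and sedation scores as primary while the Synopsis makes opioid use the only primary, and the shared opioid total includes the randomized methadone with no conversion factor

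*Combined protocol and SAP*

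**What the plan says.** **Synopsis, Outcomes.** The primary entry reads "Primary: Intraoperative and postoperative opioid utilization". The second of three secondary items is "Pain scores and pain self-assessments". Sedation appears in the Synopsis under Measurements but in neither outcome list.

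**Section 9, Primary Assessment.** Two lines stand under this heading: "Overall opioid (morphine equivalents) consumption for each patient during hospital stay" and "Absolute pain and sedation scores". The secondary list that follows has 30-day opioid consumption, pain self-assessments and CYP2B6*6 genotype. It does not contain pain scores.

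**Section 9, Statistical Analysis.** "Each cohort is analyzed separately", and then "Total daily opioid consumption and pain scores using NRS will be compared between the groups". The methods are given as "using t-test and/or analysis of variance, ANOVA and MANCOVA to account for potential cofounders". No variable is called primary, sedation is not mentioned, and no covariate is named.

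**Synopsis objective and aim 1.1.** Both name postoperative pain and opioid consumption together and do not rank one above the other.

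**Sections 6 and 7.** Methadone is the intraoperative opioid of the methadone group. Morphine equivalents are to be calculated from the electronic medical record (EMR) for the whole period from surgery to discharge. No conversion factor for methadone is given.

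**The concern.** A reader who takes the primary outcome from the Synopsis and one who takes it from Section 9 will hold the trial to different standards. If pain differs between the groups and opioid use does not, the trial has a primary finding under Section 9 and none under the Synopsis. The choice of list could be made after the data are seen.

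The item common to both lists has its own difficulty. The total includes intraoperative opioid, so in the methadone group it adds the assigned treatment to the patient's later opioid need. The Abstract and Background state the aim as reducing postoperative opioid consumption. A real postoperative saving could be hidden or exaggerated by the intraoperative component, depending on a conversion factor that the plan leaves open.

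**Working it through.** **1. The two lists side by side**

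| Item | Synopsis, Outcomes | Section 9 |
|---|---|---|
| In-hospital opioid use | primary | primary |
| Pain scores | secondary | primary |
| Sedation scores | not listed | primary |
| Pain self-assessments | secondary | secondary |

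Section 9 keeps pain self-assessments as secondary and moves only the pain scores up, so the placement does not look like a misplaced line. The changes described in Amendments 1 to 3 concern the cohorts, the 30-day questions and the numbers enrolled. None alters the ranking of outcomes, so both lists are current text.

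**2. Does the sample size show which outcome is primary?** Section 9 plans 20 evaluable subjects per methadone dose group with proportional controls. At 1:2 this is 20 + 10 = 30 per dose level. Two levels give 60 per cohort (120 in all); three give 90 per cohort (180, below the stated 200). The plan's figures are reproduced, but as a count of dose groups. No alpha, power, effect size or standard deviation is given, so the sample size points to no outcome.

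**3. What the common opioid total contains.** In morphine equivalents:

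- methadone group: (study methadone × f) + any other intraoperative opioid + postoperative opioid
- control group: intraoperative opioid + postoperative opioid

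Here f is the methadone conversion factor. Only the postoperative terms measure the response that the Abstract and Background aim at. The methadone term is fixed by the assigned dose and by f.

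To gauge its size, Background equates 20 mg with a nominal 0.3 mg/kg, which implies 20 / 0.3 = 66.7 kg. Then 0.1 mg/kg is 6.7 mg and 0.3 mg/kg is 20 mg. The documents give no f. At assumed values:

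- f = 1: 6.7 to 20 mg morphine equivalents
- f = 2: 13.3 to 40 mg

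Changing f from 1 to 2 would therefore move the group difference by 6.7 to 20 mg with no change in any patient's postoperative use. The 66.7 kg comes from a nominal inpatient dose, whereas the trial doses by ideal body weight, so these are orders of magnitude only.

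**4. Illustration of the multiplicity.** Assume, beyond the documents, two-sided 5% per test, one test each for opioid, pain and sedation, and success on any one.

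- Independent tests: 1 − 0.95³ = 14.3%.
- Common correlation ρ: 1 − ∫ φ(u) [Φ((1.96 − √ρ·u)/√(1−ρ)) − Φ((−1.96 − √ρ·u)/√(1−ρ))]³ du.

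| ρ | 0 | 0.3 | 0.5 | 0.7 | 0.9 |
|---|---|---|---|---|---|
| At least one false positive, per cohort | 14.3% | 13.6% | 12.5% | 10.9% | 8.4% |

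With one primary the figure is 5%. Section 9 fixes no scale, time point or summary for its scores, while Section 6 describes repeated assessments on two pain-intensity scales and both observed and self-rated sedation. One test per outcome is thus a lenient assumption.

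**The case against.** The strongest reply is that Section 9 may be the list that fits the trial's purpose. The Synopsis objective and aim 1.1 put pain beside opioid use, and the objective keeps its secondary goal for the 30-day data. This stands: the documents do not show that the Synopsis outcome list is right and Section 9 wrong, only that they disagree.

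It can also be said that this is a pilot with no declared alpha. That limits the error rates to illustration. It does not remove the conflict, because the plan still ranks outcomes and compares groups.

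Four stronger readings are tempting and are not supported:

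- **That no primary comparison is given.** The Synopsis and Section 2 define Group I (methadone) and Group II (control), and Section 9 compares the two groups within each cohort. With two groups, an equal-variance t-test and a one-way ANOVA are the same test (F = t²). The freedom that matters is the unnamed covariates.
- **That the daily total in the analysis paragraph is a different outcome from the hospital-stay total.** The anticipated stay is under 24 hours, so the two may nearly coincide, and the sentence may also cover the diary ("Daily home opioid usage and pain self-assessments will be recorded in a home diary"). This is loose wording, not a shown mismatch.
- **That it is unknown whether study methadone counts.** No sentence says so outright, but the Synopsis primary and Sections 6 and 7, read together, plainly include it. The clear gap is the conversion factor.
- **That any sedation difference would be a success.** The protocol treats sedation as a side effect, and a difference could mean more sedation on methadone.

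**Conclusion.** The plan is wrong as written on one point: two current sections give different primary lists, and nothing else in the document settles which governs. This rests on the text alone. The second point also stands: the opioid total common to both lists mixes the randomized drug with the response to it, and its value depends on a factor that is not stated.

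Neither point carries a firm number. A reader might infer that the trial's actual false-positive rate is 8.4% to 14.3% per cohort. It cannot be called that, since both the 5% level and the any-one-of-three rule are assumptions. The methadone amounts likewise rest on assumed conversion factors and a back-calculated weight. The documents also do not show that an intraoperative component makes the primary invalid; they show that it must be defined and reported so that the postoperative part can be seen.

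**What to change.** 1. **One list.** Make the Synopsis and Section 9 carry the same primary for each cohort. The item common to both is total opioid in morphine equivalents over the hospital stay; use that wording in the analysis paragraph for the primary comparison of methadone with control. List pain and sedation scores as secondary. Alternatively, if the sponsor keeps pain as co-primary because the objective pairs it with opioid use, state a multiplicity rule and fix one scale and one summary of the repeated scores.
2. **Study methadone.** State that it counts in the total and give its conversion factor. Also report in-hospital opioid from end of surgery to discharge separately, since that is what the Abstract and Background set out to reduce.
3. **One test.** Name a single primary test. Make any covariate-adjusted analysis a sensitivity analysis with its covariates listed.

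The cost is wording in the Synopsis and Section 9. No new data are needed, because the EMR already supplies opioid administration during surgery and until discharge. The downside is that pain and sedation may lose primary status.

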Enrolled subjects will be asked to complete a questionnaire about their current pain and what they anticipate following surgery. Patients will receive standard physiologic monitoring for anesthesia and postoperative care. Subjects within each cohort (n≥60 evaluable, depending on the number of dose levels in each cohort) are randomized 1:2 to receive either control (typical intraop opioid, such as fentanyl or morphine) or methadone HCl (0.1 – 0.3 mg/kg ideal body weight, IBW). It is anticipated that the first ten patients will receive 0.1 mg/kg IV methadone. If patients still have significant post-op opioid requirements, subsequent groups may receive 0.2 mg/kg and then 0.3 mg/kg ideal body weight.

Anesthesia and surgical care will not be altered for the purposes of this investigation, except that subjects in methadone group will receive methadone as their intraoperative opioid, rather than leaving the choice of intraoperative opioid to the anesthesiologist. The control group patients will receive intraoperative analgesia with opioids other than methadone left at the discretion of their anesthesiologist (typically fentanyl or morphine).

Administration of Study Medication

Methadone is administered as an IV bolus at induction of anesthesia. Methadone hydrochloride is available commercially for injection (10 mg/ml). Subjects randomized to the control group will receive typical (non-methadone) opioids. Both groups will receive standard of care postoperative analgesia as determined by the treating physician. Postoperative care is not altered for purposes of this study.

Assessments

Pain assessments at rest (when patient awake) will be conducted in the postoperative period by a trained member of the research team. These will occur after handoff in the Postop Anesthesia Care Unit (PACU) and approx every 15 minutes during first PACU hour, then approx every hour for the next 4 hours and at bedtime. The pain assessments will also be performed at approx 24 hrs or prior to discharge from the hospital, whichever occurs first. Pain intensity will be assessed using the 0-10 Numeric Rating Scale and a colored-visual analogue scale. Pain relief will be assessed using five point scale (0-no relief, 4-complete

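### Sedation is a primary assessment, but its only planned summary is a mean and SD, with no count of subjects who reach a given level of sedation

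*Combined protocol and SAP*

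**What the plan says.** Section 9 (Primary Assessment) lists "Absolute pain and sedation scores" beside in-hospital opioid consumption. The synopsis names only opioid utilization as primary, so sedation has this status in Section 9 alone.

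Section 6 (Assessments) says that observed sedation on the MOAA/S and the "subject's self-assessment of sedation are recorded at the same intervals as pain assessments". That schedule starts after PACU handoff and runs "approx every 15 minutes during first PACU hour, then approx every hour for the next 4 hours and at bedtime", with a last assessment at about 24 hours or before discharge. Pain is scored only in awake patients ("Pain assessments at rest (when patient awake) will be conducted in the postoperative period"). Whether that condition also limits MOAA/S scoring is not stated.

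For analysis, Section 9 gives one summary rule, "Outcome measures will be expressed by the mean and standard deviation", and one set of methods, "using t-test and/or analysis of variance, ANOVA and MANCOVA to account for potential cofounders". The sentence naming the comparisons leaves sedation out: "Total daily opioid consumption and pain scores using NRS will be compared between the groups". No worst score, threshold, count or percentage is planned for sedation, and nothing says how repeated scores are combined.

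Section 10 states: "The most common side effect of opioids such as methadone is mild sedation". A few sentences later it gives nausea and/or vomiting as methadone's most common adverse effect. Sedation is therefore among the most common effects, and the documents describe it as mild.

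**The concern.** MOAA/S is a short ordinal scale on which awake subjects are expected to score at or near the top. The safety information lies in the low tail: how many subjects became deeply sedated, how deeply, and when. A mean and SD answer none of these.

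Methadone here replaces shorter-acting opioids in patients who go home the same day or within 24 hours, and the dose may be raised between groups. A report that follows Section 9 literally could show similar mean sedation in both arms although a few methadone subjects, and no controls, had been deeply sedated. A reader could then be misled about tolerability and about differences between dose levels.

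**Working it through.** **1. The plan's own numbers.** Section 9 gives 20 evaluable subjects per methadone dose group in each cohort, with proportional controls; Section 6 gives 1:2 allocation, control to methadone. Two dose levels: 40 + 20 = 60 per cohort. Three: 60 + 30 = 90 per cohort, or 180 in all, below the stated 200. This reproduces the sample size. No alpha, power or sedation figure is given.

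**2. Scores per subject.** Handoff plus four quarter-hourly (5), four hourly, bedtime, and 24 h or discharge: 5 + 4 + 1 + 1 = 11 at most, probably fewer in same-day outpatients.

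**3. What a mean shows.** Assume a 0–5 scale with 5 = alert (not in the documents) and all other scores 5. Let k of n subjects fall to score s at d of T assessments.

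- Averaged over the stay: fall = (k/n) × (5 − s) × d / T. For 2 of 20 at score 2 once: 0.10 × 3/11 = 0.03. For 2–3 of 20 at scores 1–3, once or twice: 0.02 (0.10 × 2/11) to 0.11 (0.15 × 4 × 2/11). With T = 5: 0.04 to 0.24.
- At one time point, if all affected subjects are low together: fall = (k/n) × (5 − s), from 0.20 to 0.60, with SD 0.62 to 1.47. For 2 of 20 at score 2: mean 4.70, SD 0.92. If the two are low at different times, each time point falls by only 0.05 × 3 = 0.15.
- As a count: 2/20 = 10%, exact 95% CI 1.2% to 31.7%.

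**4. Power by simulation.** Assumptions, none from the documents: 40 v 20 subjects, 11 scores, two-sided 5% level; ordinary drowsiness (score 4) with probability 0.5 at the first four assessments and 0.2 later in both arms; affected subjects score 2 once among the first four. Repeated runs agree to within about 3 percentage points.

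| Affected, methadone v control | t-test, subject mean | t-test, one early time point | Fisher, worst score ≤2 |
|---|---|---|---|
| 10% v 0% | 7% | 5% | 4% |
| 20% v 2% | 14% | 5% | 41% |
| 35% v 5% | 33% | 7% | 78% |
| 50% v 5% | 62% | 16% | 98% |
| 35% v 5%, two low scores | 60% | 25% | 78% |

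**5. Emergence from anaesthesia.** The first score follows handoff in PACU, soon after general anaesthesia. If 30% of both arms score 2 there (assumed), t-test on subject means v Fisher on the unrestricted worst score becomes 11% v 12%, 23% v 26% and 46% v 56% for the 20% v 2%, 35% v 5% and 50% v 5% rows. With handoff shown separately and only later scores counted, Fisher returns to about 77% at 35% v 5%, provided the treatment-related low scores fall after handoff; it is lower if some occur only at handoff.

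**6. Dose level.** At 20 v 10 (assumptions of step 4), t-test v Fisher is 8% v 2% (20% v 2%) and 16% v 29% (35% v 5%). Observed counts of 2/20 v 0/10 give Fisher p = 0.54; 4/40 v 0/20 give p = 0.29. The chance of seeing at least one case in 20 is 1 − 0.95^20 = 64% at a true rate of 5%, and 1 − 0.90^20 = 88% at 10%.

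**The case against.** A reader might infer that MOAA/S is averaged over the stay, so that harm is bound to be reported as near zero. The documents do not say so. Absolute scores could equally be summarised at each time point, where several subjects low together would lower the mean visibly and widen the SD. This stands, and the 0.03 figure belongs only to the averaged reading. It does not rescue the plan: a time-point mean still gives no number of subjects affected, and step 4 shows less power at one time point because subjects are low at different times.

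A reader might also infer that a mean is the only way sedation can reach the report. That goes too far. Adverse events are to be described and reported, ORSDS and drugs given for opioid side effects are recorded, and Section 10 defines mild and severe respiratory depression. These are real but partial safeguards: deep sedation has no event definition, and ORSDS is completed once in hospital, so it cannot count low PACU scores.

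Third, the documents speak of mild sedation, and for a small general shift a mean is reasonable. That is a reason to keep the means, not to rely on them alone.

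Fourth, the simulation favours the count, since its cut-off matches the simulated event. Step 5 shows that the advantage of an unrestricted worst score largely disappears when emergence is common. This stands, and the fix needs a time window.

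**Conclusion.** The concern holds in limited form. For a repeated ordinal score named as a primary assessment, the plan specifies only mean and SD, and neither possible reading of that rule tells how many subjects were deeply sedated. The tolerability conclusion could mislead; the documents do not support saying that it would be wrong.

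The size depends on assumptions: the 0–5 scale, the event rates and the way scores are combined. With substantial differences (20% v 2% or more, 40 v 20 subjects) a worst-score comparison is clearly more powerful than a t-test on means, provided emergence is kept apart. At 10% v 0% no test has useful power and the gain is only that the count is visible. This is a cheap improvement to a pilot's reporting, not a flaw that invalidates the design.

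**What to change.** In Section 9, for MOAA/S and self-rated sedation, by arm and methadone dose level within each cohort:

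- Report the number and percentage of subjects at each score at each time point, and keep means by time point as description.
- Report each subject's worst score after the first PACU (handoff) assessment. Show the handoff score separately, since it may reflect emergence from anaesthesia.
- Give the number at or below a cut-off that the investigators fix before analysis, with a risk difference and exact 95% CI.
- Compare worst scores, methadone v control, by a rank-based or exact test. Leave dose-level results descriptive, because 20 v 10 has little power.
- State whether the awake condition on pain assessments also limits MOAA/S scoring. If it does, skipped assessments would hide the deepest sedation under any summary.

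The cost is a few lines of text and one small table from data already collected, with no added visits or subjects. There are two drawbacks: some loss of sensitivity to a small uniform shift, which the retained means still show, and deep sedation present only at handoff falls outside the worst-score test, though it appears in the separate display.

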Study Design	Single-center, randomized, single blinded, positive-controlled dose escalation pilot study. Patients receive standard monitoring for anesthesia and postoperative care. Surgical and anesthesia care (except for intraoperative opioid use) are not altered for study purposes. In each cohort, subjects are randomized 1:2 to either control (standard intraop opioid at anesthesiologists' discretion, not methadone) or methadone HCl (0.1 – 0.3 mg/kg ideal body weight, IBW). Subjects in Group I will receive methadone (IV bolus, at induction of anesthesia) as their primary intraoperative opioid. Dose of methadone may be increased up to 0.3 mg/kg IBW following preliminary analysis and review of initial subjects enrolled to Group I. Subjects in Group II (control) will receive intraoperative opioid administration at the discretion of the anesthesia providers (typically fentanyl or morphine). Postoperative pain management for both groups will be per standard of care.
Inclusion and Exclusion Criteria	
Inclusion Criteria
 
 1. Age 18-65 years 2. Undergoing general anesthesia and moderately painful, ambulatory surgical procedures, with anticipated postop stay of < 24 hours 3. Signed, written, informed consent 
Exclusion Criteria
 
 1. History of liver or kidney disease. 2. Females who are pregnant or nursing. 3. Opioid tolerant patients (e.g. preoperative methadone therapy or use of fentanyl transdermal patches) 4. History of allergy to methadone

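### The plan names no unequal-variance method for a comparison randomized 1:2, so error rates and confidence intervals are distorted if the arms differ in spread

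*Combined protocol and SAP*

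**What the plan says.** The Synopsis (Study Design) states: "In each cohort, subjects are randomized 1:2 to either control" or methadone, and Section 6 repeats the ratio. Section 9 (Sample Size) states: "Our initial plan is to enroll ≥ 60 evaluable subjects in each of two cohorts for this pilot study", and adds that "this pilot plans 20 evaluable subjects in each methadone group within each cohort, with requisite proportional controls". The overall total is given as "Anticipated total evaluable is <200".

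The efficacy comparison rests on one sentence in Section 9 (Statistical Analysis), repeated in the Synopsis: "Group outcomes will be compared across the two groups, using t-test and/or analysis of variance, ANOVA and MANCOVA to account for potential cofounders". The sentence before it reads "Outcome measures will be expressed by the mean and standard deviation". Each cohort is analyzed separately.

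The documents do not say whether the t-test pools the variances. They name no variance check, transformation or robust standard error, and give no SD for either arm, no alpha, no sidedness and no confidence level.

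On the treatments, the Synopsis says that the control group "will receive intraoperative opioid administration at the discretion of the anesthesia providers". The methadone dose ranges from 0.1 to 0.3 mg/kg ideal body weight and may be raised during the trial.

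**The concern.** A common-variance test is well protected against unequal SDs when the arms are equal in size. At 1:2 that protection is lost. The pooled variance is weighted towards the larger arm, while the true variance of the difference is driven mainly by the smaller arm. If the smaller arm (control) has the larger SD, the standard error is too small; if it has the smaller SD, the standard error is too large.

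Unequal SDs are plausible here. Opioid consumption cannot fall below zero and is expected to drop with methadone, and its SD often drops with its mean. Control opioid choice and dose are also left to the anesthesiologist. As this is a pilot, its estimates and intervals are a main product for planning later work, so their stated precision matters.

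**Working it through.** **Inputs.** From the documents: 1:2 allocation and 20 methadone patients per dose level with proportional controls. Assumed, because the documents are silent: two-sided 5% level, 95% intervals, and r = SD(control)/SD(methadone) from 0.5 to 2.

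**The plan's own figures.** One dose level is 20 + 10 = 30. Two levels give 60 per cohort (20 v 40), matching the stated minimum. Three give 90 per cohort (30 v 60) and 180 in total, within the stated ceiling of fewer than 200. There is no power calculation to reproduce.

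**Standard error at 20 v 40.** With the methadone SD set to 1:

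pooled SE² = [(19r² + 39)/58] × (1/20 + 1/40); true SE² = r²/20 + 1/40.

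For r = 2: (76 + 39)/58 = 1.983, times 0.075 = 0.1487; the true value is 0.2 + 0.025 = 0.225; √(0.1487/0.225) = 0.81. The common-variance SE is about 19% too small.

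**Type I error at 20 v 40.** Simulation, normal data, equal means, 100,000 runs per setting:

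| r | pooled SE / true SE | common-variance test | Welch |
|---|---|---|---|
| 0.5 | 1.23 | 1.8% | 5.0% |
| 1 | 1.00 | 5.0% | 5.0% |
| 1.25 | 0.93 | 6.7% | 4.9% |
| 1.5 | 0.88 | 8.7% | 5.1% |
| 2 | 0.81 | 11.2% | 5.0% |

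Repeat runs differ by about 0.2 points (for example 8.5% at r = 1.5 and 11.4% at r = 2). Results at 10 v 20 and 30 v 60 are nearly the same, so a larger trial does not remove the problem.

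**Coverage when SD is proportional to the mean.** 20 v 40, normal or log-normal data, CV 0.5 to 0.8 (assumed), 40,000 runs:

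- No effect: the SDs are equal and common-variance coverage is about 95%.
- Every methadone patient has the same expected reduction: common-variance coverage is about 92% at a 30% reduction and 88-89% at 50%. Welch gives about 93-95%; the lower values come from skewness, which Welch does not cure.
- Mixed doses with reductions of 20% and 40%: common-variance coverage about 92.5%. With 15%, 30% and 45%: about 93%. With 10% and 50%: 93-95%. With 0% and 60%: 94-97%.

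**One dose against all controls.** Group sizes are now 20 v 20 (two levels) or 20 v 30 (three levels, control larger). Under the same SD assumption, a two-group common-variance interval covers 94-95% at 20 v 20 and 96-97% at 20 v 30. In a one-way ANOVA with a single error variance and r = 2, the contrast of control with one dose has type I error 8.3% (two doses) or 6.2% (three doses). The overall F-test runs at 6.3% or 3.8%.

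**The case against.** A reader might infer that the plan gives intervals that are too narrow and p-values that are too small. The documents do not support that.

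- Pooling is not written into the t-test; the text can be read as Welch. This stands for the t-test, but not for ANOVA and MANCOVA in their standard form.
- The direction is not established. No SD is given, and methadone is not one fixed dose. With levels filled equally, the assigned mg/kg dose has a CV of 0.05/0.15 = 33% (0.1 and 0.2) or 0.082/0.2 = 41% (all three levels). Section 7 also does not say whether methadone itself enters the morphine equivalents; if it does, the methadone arm could be the more variable one. This stands.
- An SD that shrinks with the mean causes no type I inflation, because without an effect the SDs are equal. The 7% to 11% figures need unequal SDs with equal means. This stands: that mechanism affects coverage when there is an effect, not false positives.
- Dose-by-dose comparisons are distorted less, or conservatively. This stands, but the plan's sentence compares the two groups, which is where 1:2 applies.
- The plan sets no alpha or confidence level and is a pilot. This stands and lowers the severity.

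None of this is a reason to leave the method open: Welch holds its level whichever arm varies more, and the choice would otherwise be made after the data are seen.

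**Conclusion.** The point holds in conditional form. The plan names methods that assume a common variance, or leave the assumption unstated, under 1:2 allocation. If the SDs differ, error rates move in a direction that depends on which arm varies more: at 20 v 40, from about 2% (control SD half) to about 11% (control SD double) for a nominal 5% test. If the SD tracks the mean and all methadone patients share one expected reduction, 95% intervals cover about 92% at a 30% reduction and 88-89% at 50%. Mixing escalating doses lessens or removes this. All SD ratios, CVs and the 5% level are assumptions, and with equal SDs there is no error. It is a minor point and a cheap improvement.

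**What to change.** In Section 9 and the Synopsis, specify:

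- for the two-group comparison, the difference in means with a 95% CI by the Welch t-test;
- Welch ANOVA when dose groups are compared;
- HC3 heteroscedasticity-robust standard errors in any covariate-adjusted model.

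Any permutation check for skewness should use a studentized statistic. Permuting the plain difference in means does not help: at 20 v 40 with r = 2 it rejects at about 11%, like the common-variance test.

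The cost is wording only. With equal variances, power at a difference of 0.8 SD falls from 81.7% to 81.0% (40 v 20) or from 51.5% to 49.7% (20 v 10). When control varies more, the standard error is larger by 1/0.928 = 1.08 (r = 1.25) to 1/0.813 = 1.23 (r = 2; 1/0.809 = 1.24 at 10 v 20), about 8% to 24%. At 20 v 40, Welch's fewer degrees of freedom widen the interval by a further 2-3% (t multiplier 2.04 to 2.06 instead of 2.00). That extra width is what the data warrant.
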